## **9. FOLLOW-UP**

### **9.1 Follow-up of clinical investigation participants including follow-up of adverse events**

Patients will be followed up 4 weeks after end of clinical trial. If patient finished trial due to an adverse event, he will be followed up closely, namely after 7 days.

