#### **6.1.4 Duration of the clinical investigation**

Patients will stay in the study for 9 weeks consisting of 5 weeks treatment period and 4 weeks follow up period.

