#### **Follow-up of patients withdrawn from the clinical investigation**

In case of premature discontinuation after treatment with the medical device , the investigations scheduled for the EOS visit will be performed **7** days after discontinuation. The subjects will be advised that participation in these investigations is voluntary. Furthermore, they may request that from the time point of withdrawal no more data will be recorded and that all biological samples collected in the course of the clinical investigation will be destroyed.

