#### **Premature permanent discontinuation due to an adverse event**

If the reason for premature permanent discontinuation of clinical investigation is an AE, the patient should have a "Premature EOS" visit with all the assessments performed before the discontinuation of the treatment with the medical device, whenever possible.

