**BASE LINE VISIT V0**

*(Study Day 7)*

After randomization to verum or placebo group

-treatment according to randomizations: patients receive dummy or original medical device.  
Acupuncture will be performed in the concha of the ear. Patients will be instructed how to use device (eg during showering, if the patch removes etc). Device is removed by patient after 4 days.

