#### V1-V4

(Study Day 14, 21, 28, 35)

Patients receive new device, possible adverse events can be assessed, possible complications/questions can be discussed.

Day 21: 6 minutes walk test will be performed again.

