#### **Severe**

Event may cause noticeable discomfort; usually interferes with daily activities; subject may not be able to continue in the study; the AE/ADE produces sequelae, which require prolonged therapeutic intervention.

A mild, moderate or severe AE/ADE may or may not be serious. These terms are used to describe the intensity of a specific event (as in mild, moderate, or severe myocardial infarction). However, a severe event may be of relatively minor medical significance (such as severe headache) and is not necessarily serious. For example, nausea lasting several hours may be rated as severe, but may not be clinically serious. Fever of 39°C that is not considered severe may become serious if it prolongs hospital discharge by a day. Seriousness rather than severity serves as a guide for defining regulatory reporting obligations.

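### After early discontinuation, the timing of the end-of-study assessments is contradictory and the end of adverse-event follow-up is not defined

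*Combined protocol and SAP*

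**What the plan says.** Four parts of the combined protocol and SAP bear on a patient who stops early.

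- **Section 7.2.3, discontinuation due to an adverse event.** A premature EOS visit is held "with all the assessments performed before the discontinuation of the treatment with the medical device, whenever possible". The next paragraph gives the same timing for patients who stop for any other reason, and treats such a stop as withdrawal of consent.
- **Section 6.1.5, follow-up of withdrawn patients.** After any premature discontinuation following device treatment, "the investigations scheduled for the EOS visit will be performed" 7 days after discontinuation. Taking part is voluntary, and the patient may ask that no more data be recorded.
- **Section 9.1.** Patients in general are followed up four weeks beyond the end of the trial. Then: "If patient finished trial due to an adverse event, he will be followed up closely, namely after 7 days".
- **Section 6.1.4.** "Patients will stay in the study for 9 weeks consisting of 5 weeks treatment period and 4 weeks follow up period". Section 7.6.2 agrees with this and puts V5, the end-of-study visit, on Day 63.

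Devices are placed at V0 on Day 7 and at V1-V4 ("Study Day 14, 21, 28, 35"). For the V0 device the protocol states: "Device is removed by patient after 4 days". Adverse events are a secondary objective (section 5.2).

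**The concern.** Two things are unsettled. The first is when the EOS assessments take place for an early stopper: sections 7.2.3 and 6.1.5 put the same assessments on opposite sides of discontinuation, and nothing says which governs or whether both are done. The second is when adverse-event observation ends. For a patient who stops because of an adverse event, nothing after the 7-day contact is expressly scheduled. No section says when follow-up of a non-serious event closes.

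At stake is the comparability of the safety data. With 20 patients per arm, a few early stoppers can change an arm's total observation time noticeably. If stopping is related to treatment, the arm with more stoppers has less time in which further events can be recorded, and its crude count is biased downward. The assessments are affected too: an early stopper could be examined on the device, 7 days off it, or not at all, whereas a completer is examined more than three weeks after the last device comes off.

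**Working it through.** **Inputs.** First device Day 7, last placement Day 35, V5 Day 63 (section 7.6.2). Wear time is 4 days, stated at V0 and assumed to hold for the later devices. Nine weeks in all, four of them follow-up (section 6.1.4). A 7-day contact or visit after stopping (sections 6.1.5 and 9.1).

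**The plan's own figure.** 63 / 7 = 9 weeks, and 63 − 35 = 28 days = 4 weeks. Section 6.1.4 reproduces when follow-up is counted from the last placement.

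**Completers.**
- Last device off: 35 + 4 = Day 39.
- Device-free days to V5: 63 − 39 = 24.
- First device to V5: 63 − 7 = 56 days.

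**End of follow-up under section 9.1.** If the trial ends at V5, four weeks later is 63 + 28 = Day 91, which is 91 − 39 = 52 device-free days. No visit is scheduled then. If the four weeks are those of section 6.1.4, follow-up ends on Day 63.

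**Early stoppers, if the 7-day contact is the last one.** Assume the device comes off on stop day *d*. The last contact is on day *d* + 7, so there are 7 device-free days, which is 24 − 7 = 17 fewer than for a completer. Days unobserved up to Day 63 are 63 − (*d* + 7) = 56 − *d*.

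**Early stoppers, if the four-week sentence also covers them and runs from their own stop.** The last contact is on day *d* + 28. That gives 28 device-free days, not fewer than a completer's 24. Days unobserved are 63 − (*d* + 28) = 35 − *d*, or none once *d* reaches 35.

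| Stop day *d* | Last contact at *d* + 7 | Unobserved of 56 | Last contact at *d* + 28 | Unobserved of 56 |
|---|---|---|---|---|
| 7 | Day 14 | 49 (88%) | Day 35 | 28 (50%) |
| 21 | Day 28 | 35 (63%) | Day 49 | 14 (25%) |
| 35 | Day 42 | 21 (38%) | Day 63 | 0 |
| 39 | Day 46 | 17 (30%) | Day 67 | 0 |

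If instead the four-week sentence keeps every patient to Day 63 or later, nothing is lost at any stop day.

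**EOS assessments.** Under section 7.2.3 they fall 0 days after device removal; under section 6.1.5 they fall 7 days after discontinuation. This describes when the assessments are done, not the total adverse-event follow-up, because the section 9.1 contact still applies to patients who stop for an adverse event.

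**The case against.** The strongest reply is that section 9.1 fixes when a contact happens, not when follow-up stops. On that view the 7-day contact is an extra, earlier check: completers have no scheduled visit between Day 35 and Day 63, so a patient stopping for an adverse event is seen sooner after stopping than a completer is after the last device. The four-week sentence before it is not restricted to completers. This reading is reasonable, and it removes much or all of the shortfall. It is not the only reading, and the text does not choose between them.

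The reply also disposes of several stronger inferences that a reader might draw:

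- **That the highest-risk patients are watched for the shortest time.** The documents do not rank risk. Section 6.1.5 gives every early stopper the same 7 days. Section 7.2.3 gives those who stop for other reasons the same pre-removal visit, and section 9.1 gives them no 7-day contact. Their express follow-up is no longer.
- **That device removal must wait for a walk test and an echocardiogram.** The section 7.2.3 timing applies only where feasible, so it imposes no such wait.
- **That ongoing events have no route to an outcome.** Section 8.5.1 requires a follow-up report on the outcome of serious events, with no time limit, and section 8.5 records an outcome for every event. The gap is the undefined end of follow-up for non-serious events.
- **That the definition of a severe event requires longer follow-up.** Section 8.3 grades intensity and sets no observation period.

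The Day 91 point also depends on what section 9.1 means by the end of the trial. It may be loose wording, since 28 days from the last placement gives Day 63. Finally, the plan specifies no between-arm test of adverse events. That limits the inferential consequence, but counts by arm will still be read against each other.

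**Conclusion.** The concern stands as an inconsistency and a gap, not as a demonstrated bias. Sections 7.2.3 and 6.1.5 disagree on when the EOS assessments are done after an early stop. Section 9.1 leaves open whether its four weeks cover early stoppers and whether they end on Day 63 or about Day 91.

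The size depends on the reading. If the 7-day contact is the last, device-free observation is 7 days against 24, and 49 to 17 of 56 days are lost for stops from Day 7 to Day 39. If the four weeks run from the patient's own stop, the device-free shortfall vanishes and the loss is 28 days at most. If everyone is kept to Day 63 or later, there is none. These figures assume a 4-day wear time for every device and removal on the day of stopping. The effect on an arm's total depends on how many patients stop, when, and in which arm. The documents give none of these, so no arm-level figure is claimed. Crude counts become non-comparable only if stopping differs by arm.

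**What to change.** 1. Reconcile sections 6.1.4, 6.1.5, 7.2.3, 7.6.2 (V5) and 9.1 into one statement of when the EOS assessments occur relative to discontinuation, whether this differs by reason for stopping, and on which day follow-up ends. The choice of clinical rule is the sponsor's.
2. State that, unless consent to data collection is withdrawn, adverse-event and serious-adverse-event data are collected for all early stoppers up to their originally scheduled Day 63. A telephone contact is enough. This requires section 7.2.3 to separate stopping the device from withdrawing consent to data collection.
3. Report adverse events by arm with patient-days of observation beside the numbers of patients and events. Rates per patient-day do not replace item 2, because time on and off the device need not carry the same risk.

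The cost is a wording amendment, a few extra telephone contacts and one more column in the safety table.

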### **9.2 Treatment after end of clinical investigation**

Electrical auricular vagus stimulation is accessible to patients after end of clinical investigation.

## **10. STATISTICAL METHODOLOGY AND ANALYSIS**

### **10.1 Analysis sets**

Two different analysis sets are defined:

#### **Intention to treat set**

This analysis set includes subjects who were randomized and received at least one dose medical device Main analysis is by the intention-to-treat principle. Here, an outcome value is necessary for each patient, if a patient drops out. Therefore, we will use the interim assessment of walking distance after 2 weeks of treatment, or, if this is unavailable, the baseline measurement (i.e., the patient is counted as a non-responder to treatment) as replacement in such cases.

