### 5.2. Rationale of the clinical investigation

Chronic heart failure is one of the most serious medical problems in industrial countries. Despite optimized heart failure therapy the prognosis remains bad. Raised inflammatory cytokines are causing skeletal muscle fatigue and activation of muscle ergoreceptors, subsequently leading to an

increase in ventilation, sensation of breathlessness, perception of fatigue and autonomic dysbalance. Novel approaches to heart failure therapy include selective electrical vagal stimulation to normalize autonomic balance. Vagal Stimulation however remains an invasive technique, which is restricted to therapy-resistant patients. Acupuncture has been shown to act pro-vagotonic and anti-inflammatory. In addition Kristen et al recently showed an improvement of exercise tolerance in patients with HF after acupuncture treatment. A dense vagal innervation of the auricle especially of the triangular fossa and concha has been suggested by Peuker et al. La Marca R et al found an increased vagal activity after electrical acupuncture on the concha of the ear. Electrical auricular vagal stimulation is a totally new approach to therapy in heart failure. It might be a safe complementary treatment in patients with chronic heart failure. As there are no clinical studies on this topic its effects on heart failure have to be further investigated.

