### **10.2 Sample size considerations**

We assume a clinically relevant difference in the improvement in walking distance of 30 meters comparing the electrically stimulated acupuncture group to the Placebo group. Furthermore, we assume a standard deviation in the improvement of the walking distance of 30 meters (Kirsten 2010).

A sample size of 17 in each group will have 80% power to detect this clinically relevant difference between the groups using a two group t-test with a 0,050 two-sided significance level. Because of the possibility of drop-outs we include 2x20 patients.

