### **10.5 Missing, unused and spurious data**

Plausibility Checks will be performed regularly, missing data will be treated by the last observation carried forward principle.

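### A patient who dies or becomes unable to walk enters the primary ANCOVA with the Day 21 or baseline distance, so a known bad outcome is not reflected in the walk estimate

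*Combined protocol and SAP*

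**What the plan says.** The intention-to-treat paragraph of section 10.1 requires an outcome value for each patient who drops out. The first choice is an earlier walk: "we will use the interim assessment of walking distance after 2 weeks of treatment". By the visit schedule in section 7.6.2 this is the Day 21 walk, since the first device is applied on Day 7. If that walk is also missing, the plan uses "the baseline measurement (i.e., the patient is counted as a non-responder to treatment) as replacement in such cases".

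Section 10.5 adds that "missing data will be treated by the last observation carried forward principle". Section 10.6 analyses the resulting distance by ANCOVA, with baseline as covariate and treatment as factor.

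None of these sections makes the replacement depend on why the walk is missing. Death appears only as a seriousness criterion in section 8.2 and has no efficacy rule. Inability to walk is not mentioned. No worst-rank, composite or sensitivity analysis is described, and section 10.4 leaves a fuller analysis plan to be written.

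**The concern.** For an ordinary drop-out the final distance is unknown, and any replacement is a guess. For a patient who has died, or who can no longer walk because heart failure has worsened, the outcome is known and bad. The plan nevertheless enters that patient as unchanged, or with a distance measured while still on treatment.

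The Rationale section says of chronic heart failure: "Despite optimized heart failure therapy the prognosis remains bad". The same section describes the treatment as new in this disease and without clinical studies. Such events are therefore foreseeable, and an imbalance in either direction cannot be excluded. If they cluster in verum, the primary estimate can show a benefit that takes no account of them. If stimulation prevents them, the same rule hides part of its benefit.

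**Working it through.** **The plan's own figure.** Section 10.2 assumes "a clinically relevant difference in the improvement in walking distance of 30 meters" and "a standard deviation in the improvement of the walking distance of 30 meters", tested by a "two group t-test with a 0,050 two-sided significance level". The standardised difference is 30/30 = 1. The noncentral-t calculation gives 16.71, so 17 per group, with power 80.7% at 17. The statement "A sample size of 17 in each group will have 80% power to detect this clinically relevant difference" reproduces, and this point does not affect it. At the 20 per group enrolled, the same test has 86.9% power if all are observed.

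**Which replacement applies when.** From first device (Day 7) to final walk (Day 63) is 63 − 7 = 56 days. After the Day 21 walk, 63 − 21 = 42 days remain, and 42/56 = 75%. So three quarters of the time at risk falls where the Day 21 distance is carried forward. Before Day 21 the baseline distance is used and the change is exactly 0.

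**Expected ANCOVA estimate.** Let k of 20 verum patients have such an event, none in placebo, with a true gain of 30 m in the others.
- Baseline replacement: 30 × (20 − k)/20 = 28.5, 27.0 and 25.5 m for k = 1, 2, 3.
- A typical Day 21 response of 30 m carried forward: the estimate stays at 30 m for any k.
- Two events in each arm, baseline replacement: 30 × 18/20 = 27.0 m. Here the rule dilutes the effect.

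**Chance of declaring benefit.** Simulation with 20 per arm, change SD 30 m, a true gain of 30 m in the others, and baseline 350 m with SD 90 m. The baseline values are assumptions; the documents give none. The comparison is a Mann-Whitney test on change from baseline with events ranked lowest. Shares are of trials significant for benefit at two-sided 0.05:

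| Verum events (placebo 0) | Plan, baseline used | Plan, Day 21 response carried | Worst rank |
|---|---|---|---|
| 1 | about 82% | about 85–87% | about 70–73% |
| 2 | about 79% | about 85–87% | about 53–57% |
| 3 | about 75% | about 85–87% | about 31–33% |

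With no events the ANCOVA gives about 85–86%. When a Day 21 response is carried forward, the plan's result therefore hardly responds to the events.

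**How likely such counts are.** The documents give no event rate. Assume that 10–20% of patients per year die or become unable to walk, over the 9 weeks of section 6.1.4.
- Per-patient risk: p = 1 − (1 − r)^(9/52) = 0.0181 for r = 0.10 and 0.0379 for r = 0.20.
- Expected events in 40 patients: 40p = 0.72 and 1.52.
- No event at all: (1 − p)^40 = 48% and 21%.
- Exactly 2 verum and 0 placebo, same risk in both arms: 190 × p² × (1 − p)^38 = 3.1% and 6.3%.
- Three or more verum and 0 placebo: about 0.4% and 1.8%.

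The set needs at least one device application, so the window is nearer 8 weeks. The expected counts are then 0.64 and 1.35.

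**The case against.** The strongest reply is that this is a nine-week, single-centre pilot in stable NYHA II–III patients without recent ventricular tachyarrhythmia. The sentence on prognosis describes chronic heart failure in general, not the nine-week risk here. On the assumed rates, the most likely count is zero or one event, and two or three confined to one arm is unusual. That stands, and the simulated cells should be read as stress cases.

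Safety reporting also stands. Adverse events are a secondary objective, worsening of existing disease counts as one, deaths and hospital admissions are serious events, and section 6.1.6 allows termination if risk outweighs benefit. A reader might infer that harm would be invisible. The documents do not support that; the gap is confined to the walk estimate.

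Other stronger readings also fail.
- That such patients always appear unchanged or improved: a Day 21 walk can be below baseline.
- That inability to walk is as clear a case as death: the plan does not say how a patient who attends but cannot walk is recorded. Sections 6.1.5 and 7.2.3 provide end-of-study assessments around discontinuation, voluntary or where possible, which may give a real walk for some. They cannot help after a death.
- That the NYHA test is distorted: section 10.6 compares the percentage improved, and a carried-forward entry class already counts as not improved. Counting the patient as worsened changes only the descriptive table.
- That entering 0 m would show the true effect: the result would depend on a baseline distance the documents do not give. A few extreme values would also inflate the residual variance of the ANCOVA.

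**Conclusion.** The point holds. Followed as written, sections 10.1 and 10.5 give a patient who has died, or is documented as unable to walk through clinical worsening, a neutral or earlier on-treatment distance in the primary analysis. It is firmest for death. That deaths count as drop-outs is a reading of the text, but no other rule covers them.

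A reader might infer that the rule always favours verum. It does not: the between-arm bias needs an imbalance and can run either way. The size depends on assumed event counts, baseline distance and effect. Under those assumptions, two verum-only events leave the plan at about 79% for declaring benefit, or about 85–87% with Day 21 responses carried, against about 53–57% with worst-rank scoring. The chance of that split is small if the arms share the risk. The plan should be changed, but this does not invalidate the design or the sample size.

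**What to change.** In sections 10.1 and 10.5, require the reason for every missing V5 walk to be recorded, with death and documented clinical inability to walk as separate categories.

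Pre-specify, before unblinding, a supportive worst-rank analysis. Death ranks lowest and documented clinical inability to walk next. All others are ranked on baseline-adjusted change, and the groups are compared by a rank test. Report it beside the ANCOVA with the number of such events by arm.

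State the consequence in advance: if the ANCOVA is significant for benefit and the worst-rank test is not, the report says that the benefit is not robust to deaths and inability to walk. A rule triggered only when the two analyses point in opposite directions would not serve. In the simulations, no ANCOVA result significant for benefit was paired with a rank test pointing the other way. In the descriptive NYHA table, such patients can be shown as worsened.

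The cost is a few sentences and one extra analysis; sections 6.1.5 and 11.1.1 already require the reason for withdrawal in the CRF. With no such events the rank test has slightly lower power, about 85% against 87% for the t-test at 20 per arm. Settling the rule after unblinding would make the scoring of one or two deaths a data-driven choice.

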### **10.2 Sample size considerations**

We assume a clinically relevant difference in the improvement in walking distance of 30 meters comparing the electrically stimulated acupuncture group to the Placebo group. Furthermore, we assume a standard deviation in the improvement of the walking distance of 30 meters (Kirsten 2010).

A sample size of 17 in each group will have 80% power to detect this clinically relevant difference between the groups using a two group t-test with a 0,050 two-sided significance level. Because of the possibility of drop-outs we include 2x20 patients.

